University of South Carolina Protocol v4

Study Title: Evaluation of a Phone-Based Walk with Ease Program in Adults with Arthritis

Principal Investigator Name: [name]

NCT: NCT05289544

Funding: Supported by Cooperative Agreement Number U48DP006401 from the Centers for Disease Control and Prevention

Date: 6/12/2023

A.SPECIFIC AIMS

Aim 1: Identify and incorporate best practices for recruiting and retaining participants in behavioral interventions and programs, particularly among hard-to-reach populations (e.g., low socioeconomic status). A literature review will be conducted to identify best practices and recommendations for recruitment and retention strategies for hard-to-reach populations including those with low socioeconomic status. Results will be published and will help guide recruitment strategies for the proposed project.

Aim 2: Evaluate the short-term (6 weeks and 6 months) and long-term (1 year) effects of a phone-based version of Walk with Ease (WWE-T) in adults with arthritis on primary (self-reported pain and objectively measured physical function) and secondary (objectively measured physical activity, self-efficacy, depressive symptoms, weight, blood pressure, work loss, and health care utilization) outcomes as compared to a wait list control. *We hypothesize that participants randomized to WWE-T will have greater improvements in outcomes at 6 weeks, 6 months, and 1 year than those in the wait list control.*

Aim 3: Determine the effectiveness of recruitment and retention strategies in WWE-T. We will examine recruitment rates by recruitment avenue and site to determine which strategies led to greatest reach, and whether this differed by sociodemographic characteristics (e.g., age, race, income). We will also examine retention rates and reasons for attrition at program completion (6 weeks) and follow-up assessments (6 months, 1 year) by recruitment strategy among the total sample and by demographic (e.g., socioeconomic status) and clinical (e.g., pain) variables.

B. BACKGROUND AND SIGNIFICANCE

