- 8.) **Work Loss – Work Productivity and Activity Impairment Questionnaire.** The Work Productivity and Activity Impairment (WPAI) Questionnaire^{43,44} will be used to assess patient-reported amount of absenteeism, presenteeism and daily activity impairment attributable to general health as well as specifically for arthritis. The WPAI includes 6-items that assess current employment status, number of hours missed due to a health problem or other reasons, hours actually worked, degree to which health affected productivity while working, and the degree to which health affected regular (nonwork) activities. Four outcome scores will be calculated: percent work time missed due to health, $Q2/(Q2 + Q4)$ (percentage of absenteeism); percent impairment while working due to health, $Q5/10$ (percentage of presenteeism); percent overall work impairment due to health, $Q2/(Q2 + Q4) + [(1 - Q2/(Q2+Q4)) \times (Q5/10)]$; percent activity impairment due to health, $Q6/10$. Higher scores for each outcome score (range 0–100%) suggest a greater impact of health. The WPAI has found to be a valid assessment of work-related impairments in populations with arthritis⁴⁵ and its use is recommended by the rheumatology community.⁴⁶
- 9.) **Health-care utilization and Medical Expenditures.** While access to medical records would provide a more accurate assessment of healthcare utilization and expenditures, it would not be feasible to obtain among our community-dwelling population due to the time and costs associated with obtaining and reviewing charts, healthcare visits may be with multiple providers and not all tracked, and due to privacy concerns.⁴⁷ Self-report assessments of healthcare utilization have been found to be both valid and reliable among older adults⁴⁸ and have a low likelihood of bias by demographic factors including socioeconomic status.⁴⁷ Therefore, we

University of South Carolina Protocol v4

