propose to use the UCSD Healthcare Utilization Questionnaire⁴⁹ to estimate health care utilization during the study. This survey consists of 12 questions that asks participants to report the number of times they used different healthcare services within a specific timeframe. Specifically, questions assess physician visits or telephone calls with health care providers, home-care visits, ambulance use, inpatient hospital days, surgeries, emergency room visits, and medication use. The costs associated with each health care utilization will be obtained from the Medical Expenditure Panel Survey (MEPS).⁵⁰

- 10.) **Physiological outcomes – Blood Pressure.** Systolic and diastolic blood pressure will be measured according to the American Heart Association guidelines in triplicate each visit using an osillometric blood pressure cuff (Omron, Tampa Bay, FL) on the left arm at each visit in the supine position after a 5-minute rest in a quiet room. The average of the all three measures in mmHg will be used in analyses.^{51,52}
- 11.) **Demographic and Health Variables.** At baseline, participants will be asked to complete general demographic and health history surveys. The demographic variables to be assessed include age, sex, race, ethnicity, education, income, and marital status. The health history survey will include an assessment of arthritis type, years since arthritis diagnosis, presence of comorbid chronic health conditions (e.g., hypertension, hyperlipidemia), prescription and over-the-counter medications and doses, number of physician visits in the past 4 months, hospitalizations in the past month, and smoking status.
- 12.) **Process Measures & Program Evaluation.** WWE-T leaders will track phone session attendance for both individual and group calls. The percentage of calls attended will be calculated for each participant (total calls attended/12 calls). Topics discussed and duration of each call will also be tracked. Following the completion of WWE-T, participants will complete the Walk with Ease Post-Program Evaluation.⁵³ This evaluation asks participants to rate usefulness of tools and strategies provided, knowledge obtained, length of the program, and their overall satisfaction with the program using a Likert scale from 0 (not at all) to 3 (very well). Additional questions will be added specific to the phone-based program including satisfaction with group and individual calls, length of group and individual calls, and rapport with WWE-T leader.

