Data Analysis: After data collection and cleaning, baseline characteristics of the groups will be compared. Variables which differ between the groups at baseline will be used as covariates in the outcome models. For each of the Aim 2 primary and secondary outcomes, a generalized linear model will estimate group means at baseline, six weeks, six months and one year. Each model will include factors for group (2 levels), time (4 levels), group-by-time interactions and the required covariates. In the event of participants being lost to follow-up or otherwise missing data from the 6-week, 6-month and/or 1-year times, the models will provide estimates using Full Information Maximum Likelihood with robust standard errors, interpretable under an Intent to Treat principle.

For each outcome at each follow-up time, a statistically significant (at the 0.05 level) group by time interaction in the hypothesized direction will be interpreted as supporting the research hypothesis. The magnitude of each intervention effect will be computed by a pre-defined contrast of baseline to follow-up change in the group minus baseline to follow-up change in the Wait List Control, adjusted for covariates. All four time points for each outcome will be examined with a single model to best account for the full covariance structure over time. All analyses will be completed using SAS (SAS Institute Inc, Cary, NC).

We will evaluate the recruitment and retention strategies used during the proposed study, focusing on successful strategies used to increase participation of adults with arthritis, particularly among those with low socioeconomic status. During the recruitment and screening of participants, participants will be asked to report how they heard of the program. We will also examine recruitment numbers over time in relation to recruitment activities. Following the completion of the program, we will categorize recruitment avenues (e.g., saw flyer, word of mouth) and sites (e.g., local rheumatologist site, lupus support group) and calculate the percentage of those screened, not interested, ineligible, and enrolled. Percentages will be calculated among the total sample recruited as well as specifically for those of low

University of South Carolina Protocol v4

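### Secondary outcomes are read as supporting the hypothesis on the same unadjusted per-outcome, per-visit rule as the primaries, so the chance of at least one false secondary claim is well above 5%

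*Combined protocol and SAP*

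**What the plan says.** Section C, Data Analysis, puts all Aim 2 outcomes under one model and one rule. The scope is stated first: "For each of the Aim 2 primary and secondary outcomes, a generalized linear model will estimate group means". The test comes next: "For each outcome at each follow-up time, a statistically significant (at the 0.05 level) group by time interaction in the hypothesized direction". The plan then fixes what such a result means, namely that it "will be interpreted as supporting the research hypothesis".

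Section A, Aim 2, names the "secondary (objectively measured physical activity, self-efficacy, depressive symptoms, weight, blood pressure, work loss, and health care utilization) outcomes". That is seven domains. The Study Design paragraph in section C gives the same seven, with weight listed twice. The Aim 2 hypothesis covers outcomes in general: participants given the program "will have greater improvements in outcomes at 6 weeks, 6 months, and 1 year" compared with the wait list control.

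Three of the seven domains have more than one possible score (section C, Measures):

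- **Blood pressure (item 10):** systolic and diastolic values.
- **Work loss (item 8):** "Four outcome scores will be calculated", with impairment attributed both to general health and to arthritis.
- **Health care utilization (item 9):** a 12-question survey whose "questions assess physician visits or telephone calls with health care providers, home-care visits, ambulance use, inpatient hospital days, surgeries, emergency room visits, and medication use", with costs attached afterwards. No summary score is named.

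No section says which score decides any of these domains. No section gives a multiplicity adjustment, a testing order, a gate on the primary result or an exploratory label. Section D, Sample Size, computes power for the primary outcomes only.

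**The concern.** Leaving secondary outcomes unadjusted is common and defensible when they are presented as supportive. Here the plan gives a favourable secondary result at 0.05 the same interpretive weight as a primary result. The primary/secondary labels play no part in the decision rule.

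If pain and physical function were null, the plan as written would still let a single favourable secondary outcome at one visit be reported as support for the research hypothesis. With 21 or more such opportunities, some will arise by chance. Where a domain has several scores and none is designated, the choice could also be made after the data are seen without departing from the plan.

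**Working it through.** **1. The plan's own figure.** Sample Size gives at least 80% power with 120 per group, d = 0.37 and significance level 0.05. A two-sample t-test reproduces this: 81.4% two-sided (normal approximation 81.8%). One-sided, the normal approximation gives 88.9%. Sidedness is not stated. The two-sided value lies closer to the stated 80%, so two-sided 0.05 is assumed below, but the power statement does not settle the matter.

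**2. False-claim rate per test.** The rule needs significance at 0.05 and a "group by time interaction in the hypothesized direction". Two-sided 0.05 with only the favourable tail counted gives 0.05 / 2 = 0.025 per test.

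**3. Number of tests.** The smallest reading is one score per domain: 7 domains x 3 follow-up times = 21 tests. A fuller reading counts MVPA 1 + self-efficacy 1 + depressive symptoms 1 + weight 1 + blood pressure 2 + WPAI 4 + utilization categories 7 = 17 scores, so 17 x 3 = 51 tests. The 17 is an inference; the rule says outcome, not score.

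**4. Independent tests, as an upper reference.** The chance of at least one false claim is 1 - (1 - 0.025)^m.

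- m = 21: 1 - 0.975^21 = 0.41, with 21 x 0.025 = 0.53 false claims expected.
- m = 51: 1 - 0.975^51 = 0.73, with 51 x 0.025 = 1.28 expected.

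**5. Correlated tests.** The documents give no correlations, so these are assumed. Test statistics were simulated as multivariate normal under no effect, with the correlation between two tests equal to the between-time value times the between-outcome value. A false claim is any z > 1.96.

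| Between times | Between outcomes | 21 tests | 51 tests |
|---|---|---|---|
| 0.5 | 0 | 36% | 67% |
| 0.5 | 0.3 | 30% | 50% |
| 0.5 | 0.5 | 26% | 39% |
| 0.5 | 0.8 | 17% | 23% |
| 0.8 | 0.8 | 13% | 18% |

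**6. Gated reading.** The rule could mean that an overall 3-df group-by-time test must be significant at 0.05 before a visit's contrast counts. With correlation 0.5 between times and 0.5 down to 0 between outcomes, the chance is 10% to 13% for 7 scores and 18% to 29% for 17 scores.

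**7. One-sided reading.** If 0.05 were one-sided, the rate per test would be 0.05, and 21 independent tests would give 1 - 0.95^21 = 66%. The figures above are therefore the more lenient choice on sidedness.

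**The case against.** The strongest reply is that the plan does rank its evidence: outcomes are labelled primary or secondary, and only the primaries drive the sample size. The rule is also stated outcome by outcome and visit by visit, so a significant result can be read as support for that outcome at that visit only. On that view no family spans weight, mood and blood pressure, and formal error control for secondaries is partly a matter of preference. It stands that the documents nowhere say one result establishes a whole domain. But the labels do not enter the rule, and Aim 2 states a single hypothesis covering all outcomes and visits. Fitting all visits in one model handles covariance over time; it does not limit error across visits or outcomes.

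Three stronger readings are tempting and are not supported:

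- **That the plan tests every score.** The rule refers to outcomes. The utilization section lists what a questionnaire asks, not seven separate outcomes. What the text supports is an undefined deciding score.
- **That a false secondary claim is likely.** At moderate correlation the chance is 26% to 39%. It passes 50% only with larger test counts and little or no correlation, or with one-sided testing. Zero correlation is implausible for the WPAI scores, because overall work impairment is built from absenteeism and presenteeism.
- **That the PROMIS, HAQ, fatigue and stiffness measures add claims on the same terms.** They are named in neither Aim 2 list, and the rule is confined to Aim 2 outcomes.

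**Conclusion.** The concern holds in a limited form. The plan gives secondary results the same confirmatory reading as primary results, without adjustment, order or gate. On the smallest count (21 tests, two-sided 0.05 with only favourable results counted, no true effect), the chance of at least one false supporting result is about 26% at correlations of 0.5. It runs from about 13% (all correlations 0.8) to 36% (uncorrelated outcomes, 0.5 between times). An overall interaction gate would bring it to about 10% to 13%. If 17 scores were each tested without a gate, it would be about 39% (18% to 67%), but that count is not fixed by the documents.

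The correlations, the sidedness and the number of scores are all assumptions. Every combination examined stays above 5%. A reader might infer that a false claim is more likely than not; that holds only on some readings and should not be asserted. The sample size is unaffected, because it rests on the primary outcomes.

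**What to change.** 1. In Data Analysis, confine the rule that reads a significant result as support for the hypothesis to the primary outcomes. State that secondary outcomes are supportive and will be reported as estimates with 95% confidence intervals.
2. Align the Aim 2 hypothesis in section A, which now covers all outcomes.
3. In Measures, name one deciding score each for blood pressure, work loss and health care utilization. This step alone is not enough: 21 tests would remain.
4. If confirmatory secondary claims are wanted, name one score and one visit per domain and test them by Holm or in a fixed sequence, only after primary success. Primary success would then have to be defined, since the same per-outcome, per-visit rule now governs the primaries. With seven tests the first Holm threshold is 0.05 / 7 = 0.0071; at d = 0.37 and 120 per group, power at that threshold is about 57%.

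Steps 1 to 3 cost wording in three places and need no extra data or participants. The downside is that an isolated significant secondary result can no longer be presented as confirming the hypothesis.

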Exclusion Criteria: Participants will only be excluded if they have any contraindications to exercise (besides arthritis) per the Physical Activity Readiness Questionnaires,⁵⁶ are pregnant, breastfeeding, or planning to become pregnant in the next year, have a serious cognitive impairment, or are currently or have previously participated in a WWE program within the last 12 months.

Sample Size: In order to assure sufficient statistical power to detect clinically meaningful effects, we relied on information from a previous study by Wilcox, et. al.¹¹ for an estimate of variability in the VAS Pain scale and physical function tests including the 30-second chair stands and six-minute test. The Steps to Health study evaluated two 12-week self-directed multicomponent exercise programs for adults with arthritis.¹¹ Clinically meaningful magnitude of changes were suggested by Bennell et al.⁵⁷ as 11 points for VAS pain, 1.3 repetitions for the chair stand test and 20-50 meters for the six-minute walk. Estimated power is based on a simplified analysis (t-tests) without covariate adjustments. A statistical significance level of 0.05 was used.

A sample of 120 participants per group would provide 80% or greater power to detect a clinically meaningful difference in each primary outcome, with a minimum effect size of $d=.37$, assuming that the variability within our sample is comparable to that observed in the earlier study from a similar population (see Table 2). We anticipate that some participants may be lost to follow-up before the conclusion of the study. Therefore, we propose inflating the required sample size by 25% to account for potential attrition and recruiting 300 participants total, with 150 to be randomized into each treatment condition.

2.RECRUITMENT PLANS:

Participants will be recruited using effective recruitment strategies used in the past as well as with the assistance of DHEC, the SC Department of Aging, and Lupus Foundation of America across Richland,

University of South Carolina Protocol v4

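### Letting each arm have its own baseline mean makes the change-from-baseline contrast unbiased but needlessly imprecise; whether power drops below 80% depends on an SD and a correlation that the protocol does not state

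*Combined protocol and SAP*

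**What the plan says.** In section C, Data Analysis, for each Aim 2 outcome, "a generalized linear model will estimate group means at baseline, six weeks, six months and one year". The terms are listed: "Each model will include factors for group (2 levels), time (4 levels), group-by-time interactions and the required covariates". The effect at each follow-up is a "pre-defined contrast of baseline to follow-up change in the group minus baseline to follow-up change in the Wait List Control", adjusted for covariates. The covariates are chosen from the data: "Variables which differ between the groups at baseline will be used as covariates in the outcome models". Missing follow-up is handled by "Full Information Maximum Likelihood with robust standard errors, interpretable under an Intent to Treat principle". Nothing constrains the arms to a common baseline mean, and the baseline value of the outcome is not named as a covariate.

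Under Randomization, also in section C, allocation (1:1) follows completion of the baseline assessment.

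In section D.1, Sample Size, 120 per group is said to give at least 80% power for each primary outcome at a minimum effect size of d = .37, with recruitment raised by 25% to 150 per group. "Estimated power is based on a simplified analysis (t-tests) without covariate adjustments". "A statistical significance level of 0.05 was used". The variability comes from an earlier exercise trial. The text does not say whether the SD is of scores or of change, and gives no baseline/follow-up correlation. The table it cites is not in the text available to me.

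**The concern.** Because baseline precedes randomization, any observed difference in baseline means is chance. A model that estimates the two means separately and then subtracts them carries that chance difference at full weight into every effect estimate. A model with one common baseline mean, or one that adjusts for the baseline outcome, subtracts only the part that predicts follow-up.

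The same contrast serves both primary domains at three follow-ups, and the secondary outcomes as well. At stake is precision throughout, and possibly the power claim: the t-test in Sample Size and the change contrast in Data Analysis have the same variance only if the SD used was the SD of change, or if r happens to be 0.5.

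**Working it through.** **Inputs from the documents.** 120 per group with follow-up, 150 per group randomized, d = .37, significance level 0.05, 1:1 allocation. **Assumptions.** Two-sided test; continuous outcome with equal variance at each time; one follow-up time considered at a time; r not given, so varied. Power uses the noncentral t with 238 degrees of freedom; a normal approximation differs by less than 0.4 points.

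**1. The plan's own figure.** With 120 per group and d = .37, power is 81.4%, which agrees with the stated 80% or greater. Also 120 × 1.25 = 150. Both reproduce.

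**2. Variance per arm, in units of the score variance.**
- Planned contrast, 120 completers: 2(1−r)/120.
- Planned contrast by full-information likelihood, 150 baselines and 120 follow-ups: (1−r²)/120 + (1−r)²/150.
- Common baseline mean (or baseline-adjusted): (1−r²)/120.

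The ratio of the third to the first is (1−r²)/[2(1−r)] = (1+r)/2, which is below 1 for every r below 1.

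Worked at r = 0.3 under likelihood: planned 0.91/120 + 0.49/150 = 0.00758 + 0.00327 = 0.01085; common baseline 0.00758; ratio 0.70.

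| r | Ratio, completers | Ratio, likelihood 150/120 |
|---|---|---|
| 0.3 | 0.65 | 0.70 |
| 0.5 | 0.75 | 0.79 |
| 0.7 | 0.85 | 0.88 |

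These ratios do not depend on how d was scaled.

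**3. Power if d = .37 is on the score SD (assumption).** The noncentrality is .37/√(2 × variance per arm).

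| r | Planned, 120 completers | Planned, likelihood 150/120 | Common baseline |
|---|---|---|---|
| 0.3 | 67.5% | 70.6% | 84.9% |
| 0.4 | 74.1% | 76.7% | 87.6% |
| 0.5 | 81.4% | 83.4% | 90.9% |
| 0.7 | 95.8% | 96.3% | 97.9% |

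Planned power crosses 80% at r of about 0.48 with 120 completers, about 0.45 under the likelihood analysis, and about 0.35 if all 150 per arm are followed. The common-baseline figure is never below the 81.4% in step 1, since 1−r² cannot exceed 1.

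**4. Power if d = .37 is on the SD of change.** The planned contrast with 120 completers keeps 81.4% at every r, and the likelihood analysis does slightly better, so there is no shortfall. A common baseline still raises power, to 90.9% at r = 0.5 and 87.2% at r = 0.7.

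**5. Does the planned covariate adjustment recover the loss?** Not reliably. A covariate enters only if it differs between arms at baseline, so the baseline outcome has no assured place. A covariate entered as a main effect shifts all four times equally, so with complete data it cancels from a difference in change.

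**The case against.** The case for leaving the plan alone has real strength.

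- The contrast is pre-specified, matches the Aim 2 hypothesis of greater improvement, and is unbiased under randomization. That stands. A reader might infer that chance baseline imbalance biases the result through regression to the mean; it does not on average over randomizations. It is the same loss of precision seen from another side.
- A reader might infer that the plan uses an unadjusted difference in change. It does not: the contrast is adjusted for covariates. The weakness is how those covariates are chosen and what a main effect can do to a change contrast.
- A reader might infer that the trial falls short of 80% power, or does so whenever r is below 0.5. The documents do not support this. They give no r and do not identify the SD; Sample Size describes its clinical targets as changes, so an SD of change is possible. The value 0.5 is where the change contrast and a follow-up-only t-test have equal variance, not where power reaches 80%. Above 0.5 the planned contrast beats the stated power. Also, .37 is the smallest effect size among the primary outcomes, so any with a larger d has more margin.
- Completer-only figures overstate the loss, because the likelihood analysis also uses the baselines of people later lost. That stands, and the 150/120 figures are the ones to rely on.
- The formulas do not carry over directly to secondary outcomes that are counts of health care use or percentages of work impairment. That also stands.

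None of this gives a reason to estimate two baseline means when randomization says there is one.

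**Conclusion.** The planned analysis is valid but less precise than it could be, and the gain is available under either reading of d. For continuous outcomes with equal variance over time, a common baseline mean cuts the variance by about 30%, 21% and 12% at r = 0.3, 0.5 and 0.7 under the planned likelihood analysis with 150 baselines and 120 follow-ups per arm.

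A power shortfall is possible but not shown. It requires d = .37 to be on the score SD and r to be under about 0.45; neither can be settled from the documents. This is a recommended improvement, not a flaw that threatens the trial's conclusions.

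**What to change.** In Data Analysis, keep the single four-time-point likelihood model, but drop the group difference at baseline so that both arms share one baseline mean, and keep the group terms at the three follow-ups. Define each effect as the WWE-T minus wait-list difference at 6 weeks, 6 months and 1 year from that model. Under randomization this targets the same quantity as the planned contrast, so the hypotheses are unchanged.

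For count or percentage outcomes, model the follow-up values in a suitable generalized linear model with the baseline value as a covariate. This is not interchangeable with the common-baseline model when data are missing: a follow-up-only model omits participants with no follow-up, whereas the common-baseline model keeps their baselines.

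In Sample Size, state whether the SD behind d = .37 is of scores or of change and, if of scores, the r assumed for each primary outcome.

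The cost is a few sentences and a small change to the SAS model statement. No new data or participants are needed. The change should be documented before outcomes are compared by arm.

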socioeconomic status (i.e., income <150% of poverty guidelines) and other demographic (e.g., race) or clinical variables (e.g., pain). We will compare enrollment yields by avenues and sites, using total sample and those with low socioeconomic status, using chi-square tests or Fisher's exact test if cell frequencies are less than 5. Identifying the highest yielding recruitment sources, especially for those with low socioeconomic status, will help to inform recruitment strategies used in future programs. Retention of participants in WWE-T will be examined at program completion (6 weeks) and each follow-up assessment (6 months and 1 year). Overall retention rates and percentages of specific reasons for attrition (e.g., loss to follow-up, no longer interested, medical issues) will be calculated among the total sample and by those with low socioeconomic status (i.e., income <150% of poverty guidelines), and other demographic (e.g., race) or clinical variables (e.g., baseline pain). We will also examine retention and specific reasons for attrition based on recruitment avenue and site. Independent samples t tests and chi-square tests (or Fisher's exact test for those with cells less than 5) will be used to examine differential attrition.

Data Management: All surveys will be administered via paper or online via REDCap (secure, web application for building and managing online surveys and database – managed by Health Sciences South Carolina). Any paper documents will be stored in a locked filing cabinet at the TecHealth Center at University of South Carolina. All computer files will be password protected. Only the study team will have access to the data.

D. PROTECTION OF HUMAN SUBJECTS

1.TARGET POPULATION

Inclusion Criteria: The target population will include adults ≥ 18 years old who meet criteria for the CDC's definition of self-reported arthritis.^{54,55} Specifically, participants who respond yes to the following question will be eligible: "Have you ever been told by a doctor or other health professional that you have some form of arthritis, rheumatoid arthritis, gout, lupus, or fibromyalgia?" Additionally, participants must be able to read and write in English, plan to live in the Columbia, SC region for the next year, complete all baseline measures, and be willing to be randomized to either study condition.

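### Aim 3 asks whether recruitment reach by avenue and site differs by age, race and income, but no planned recruitment test compares those groups

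*Combined protocol and SAP*

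**What the plan says.** Section A, Aim 3, has two parts. The first is "We will examine recruitment rates by recruitment avenue and site to determine which strategies led to greatest reach". The second asks "whether this differed by sociodemographic characteristics (e.g., age, race, income").

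Section C, Data Analysis, sets out the recruitment analysis. For each avenue and site the team will "calculate the percentage of those screened, not interested, ineligible, and enrolled". The percentages are given for the whole sample, for low "socioeconomic status (i.e., income <150% of poverty guidelines) and other demographic (e.g., race) or clinical variables (e.g., pain"). One set of recruitment tests follows: "We will compare enrollment yields by avenues and sites, using total sample and those with low socioeconomic status, using chi-square tests or Fisher's exact test", with Fisher's test reserved for small cells. The stated use is "Identifying the highest yielding recruitment sources, especially for those with low socioeconomic status, will help to inform recruitment strategies used in future programs".

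The t tests and chi-square tests that close the same section concern differential attrition, not recruitment yield. No power figure or significance level is stated for Aim 3.

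**The concern.** The second part of Aim 3 is a between-group question. Its null hypothesis is that the avenue pattern is the same in each group, that is, no avenue-by-group interaction. The planned tests have a different null: that all avenues have equal yield within the set analysed. One set contains the other, so low-SES people are never compared with anyone else. Reading the sentence as total sample against low SES does not help, because those sets overlap.

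A team that wants to answer the second part therefore has only two overlapping p-values and the percentages. The p-values invite comparison, but the low-SES test is based on fewer people and the total-sample test is partly driven by the same people. At stake is the advice to future programs on reaching low-SES groups, which the plan gives as the purpose of this analysis.

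**Working it through.** **What each analysis tests**

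| Aim 3 names | Recruitment test planned | Compares the groups? |
|---|---|---|
| Overall reach by avenue and site | Chi-square/Fisher, total sample | Not needed |
| Income | Chi-square/Fisher within low SES | No |
| Race | None; percentages only | No |
| Age | None; not named in the recruitment analysis | No |

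**Inputs.** The documents give no screening numbers, avenue sizes or yields, so these are assumptions: 600 screened (range 450 to 900), four equal avenues, half low-SES (also 80%), two-sided 0.05. The critical value of chi-square on 3 df is 7.81. For yields p_k with n_k people per avenue and mean yield m, the noncentrality of the avenue test is λ = Σ n_k(p_k − m)² / [m(1 − m)]. Joint results come from simulation, with a likelihood-ratio test of avenue-by-SES in a logistic model.

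**(a) Same pattern in both SES groups: 40/45/55/60%.** Here m = 0.5 and the squared deviations sum to 0.01 + 0.0025 + 0.0025 + 0.01 = 0.025.
- Total sample: λ = 150 × 0.025 / 0.25 = 15.0, power 92%.
- Low SES, half the sample: λ = 75 × 0.025 / 0.25 = 7.5, power 62%.
- Simulated disagreement between the two tests: about 31% at 600 screened (about 36% at 450, 17% at 900), nearly all significant in the total and not in low SES. The interaction test rejects in about 5%.
- If 80% are low-SES: λ in the subset = 120 × 0.025 / 0.25 = 12.0, power 84%. Disagreement falls to about 11%.

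A single table shows the mechanism. Take two avenues with 82/150 and 68/150 enrolled in each SES group. In the total, the difference is 28/300 = 0.093, SE = √(0.25 × 2/300) = 0.041, z = 2.29, p = 0.022. In low SES the difference is the same, SE = √(0.25 × 2/150) = 0.058, z = 1.62, p = 0.11. The interaction is exactly zero.

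**(b) Avenues matter only for low SES: 30/43/57/70% against a flat 50%.**
- Total yields average to 40/46.5/53.5/60%. Squared deviations sum to 0.02245, so λ = 150 × 0.02245 / 0.25 = 13.47, power 88%.
- Low SES: squared deviations sum to 0.0898, so λ = 75 × 0.0898 / 0.25 = 26.94, power 99.6%.
- Both tests are significant in about 88%, which looks like agreement. The interaction test rejects in about 90%.

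**(c) A more modest difference: 40/45/55/60% in low SES only, flat 50% in others.** With 75 per cell in each group, the noncentrality of the group-by-avenue contrast on the yield scale is approximately (75 × 75/150) × 0.025 / 0.25 = 3.75. The interaction test then has power of only about 33% at 600 screened.

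**The case against.** The strongest objection is that the documents never say the two p-values will be compared. A reader might infer a rule that SES matters when one test is significant and the other is not, and conclude that the results will mislead in both directions. The documents state no such rule. Their stated use is finding high-yield sources overall and for low SES, and the planned tests suit that use. This stands: the results *can* mislead if used for the second part of Aim 3.

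Second, percentages by subgroup are planned, and on average they point the right way. In (a), total and low-SES yields are identical. In (b), 40/46.5/53.5/60% sits beside 30/43/57/70%, so an attentive reader could see a difference. This also stands in part, but the total is diluted by the low-SES people in it, and no intervals or non-low-SES column are specified.

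Third, a reader might take Section D.2 to mean that about half of those screened will be low-SES. It sets a floor of 50% on people who are both aged 18–64 and low-SES, among recruits. It says nothing about the screened denominator, so the 31% figure depends on an assumed share.

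Fourth, a reader might infer that an interaction test recovers nearly all the lost information. The 90% power in (b) rests on a 40-point spread. With a 20-point spread it is about 33%, and many unequal avenues would lower it further.

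**Conclusion.** The mismatch holds from the text alone: the second part of Aim 3 has no matching recruitment test for income, race or age. How far the planned tests could mislead is conditional. Under the stated assumptions with an identical pattern, they disagree in about 31% of trials with half low-SES and about 11% with 80%, against 5% for a direct test. With a large difference confined to low SES, they agree in being significant in about 88%. These rates depend on assumed screening numbers, yields and SES share.

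The documents do not support saying that the planned tests are invalid or that a real difference will necessarily be missed. This is a process aim, and the Aim 2 treatment comparison is unaffected. The change is still worth making, because it is cheap and the result is meant to guide later recruitment.

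**What to change.** In Section C, Data Analysis:

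1. Keep the total-sample and within-low-SES tests, and say that they address which sources yield most.
2. For whether this differed, report yields by avenue and by site for low-SES and non-low-SES people side by side, with confidence intervals for the differences. Test avenue-by-SES, and likewise site-by-SES, in a logistic model of enrolled (yes/no). Pool sparse avenues or use an exact or penalised version. Do the same for age group (for example the <65/≥65 split already used for stratification) and race.
3. State whether income is recorded at screening. Section C, Measures, item 11, lists it in the baseline survey. If it is known only for enrolled participants, compare the distribution of avenues and sites between low-SES and non-low-SES enrollees with a chi-square or Fisher test. That describes who came from where rather than yield. The planned low-SES yield test needs the same screening data.
4. State that estimates with intervals lead, and that a non-significant interaction will not be read as no difference.

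The cost is plan wording and a few models, with no extra participants or visits, provided that income, age and race are held for those screened. The downside is limited power for modest differences, and some avenues will have to be pooled.
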